3.5.2.2 Serious adverse events

Information about all serious adverse events will be collected and recorded on the Serious Adverse Event Report Form. To ensure patient's safety each serious adverse event must also be reported to IQVIA within 24 hours of learning of its occurrence. IQVIA on its turn will promptly inform Recordati. A serious adverse event is an undesirable sign, symptom or medical condition which:

1. is fatal or life-threatening
2. required or prolonged hospitalization
3. results in persistent or significant disability/incapacity
4. constitutes a congenital anomaly or a birth defect
5. is medically significant, in that it may jeopardize the subject and may require medical or surgical intervention to prevent one of the outcomes listed above.

Events not considered to be serious adverse events are hospitalizations for the:

- Routine treatment or monitoring of the studied indication, not associated with any deterioration in condition
- Social reasons and respite care in the absence of any deterioration in the patient's general condition
- Elective or pre-planned treatment for a pre-existing condition that is unrelated to the indication under study and has not worsened since signing the informed consent

Any serious adverse event occurring after the patient has provided informed consent or acknowledged an equivalent document (e.g., written information) as per country regulation and until 28 days after the patient has completed the 3-year observation period or up to 3 months after the last dose of pasireotide s.c. for patients who permanently discontinue pasireotide s.c. prior to completing 3-year observation period must be reported.

Serious adverse events occurring more than 28 days after the patient has completed the 3-year observation period or more than 3 months after pasireotide s.c. discontinuation for patients who permanently discontinue pasireotide s.c. prior to completing the 3-year observation period need only be reported if a relationship to pasireotide s.c. is suspected. Instructions about completing initial and follow-up Serious Adverse Event Report Forms and sending them to IQVIA are given in [Section 7.1.1](#) (Instructions for rapid notification of serious adverse events).

Information about all SAEs is collected and recorded on the Serious Adverse Event Report Form. The investigator must assess and record the relationship of each SAE to pasireotide s.c., complete the SAE Report Form in English, and send the completed, signed form by email within 24 hours to IQVIA Safety Office.

The telephone and telefax number of the contact persons in the local IQVIA Safety Office, specific to the site, are listed in the investigator folder provided to each site. The original copy of the SAE Report Form and the fax confirmation sheet must be kept with the case report form documentation at the study site.

Follow-up information is sent to the same person to whom the original SAE Report Form was sent, using a new SAE Report Form stating that this is a follow-up to the previously reported SAE and giving the date of the original report. Each re-occurrence, complication, or progression of the original event should be reported as a follow-up to that event regardless of when it occurs.

The follow-up information should describe whether the event has resolved or continues, if and how it was treated, and whether the patient continued or withdrew from study participation.

3.5.2.3 Adverse events of special interest (AESIs)

Adverse events of special interest consist of AEs for which there is a specific interest in connection with pasireotide treatment (i.e. where pasireotide may influence a common mechanism of action responsible for triggering them). The adverse events of special interest may require reporting additional information and completion of the event-specific checklists and/or questionnaires.

For pasireotide s.c. the following risks are specified as important identified risks: hypocortisolism/cortisol withdrawal syndrome, hyperglycemia, bradycardia, QTc interval prolongation, cholelithiasis, hematological abnormalities, increased liver enzymes, injection site reactions, and gastrointestinal disorders. The following risks are identified as important potential risks for pasireotide s.c.: clinically significant GH/IGF-1 decrease, hypothyroidism, pancreatitis, coagulation abnormalities, hypotension, hypocalcemia, gastrointestinal erosions/bleedings, potential interactions with cyclosporine, drugs metabolized by CYP3A4, bromocriptine, antiarrhythmic medicines and antidiabetics, off-label use in children and other indications, allergic reactions/immunogenicity, and tumor expansion. These important risks represent but are not limited to the AESIs.

Targeted follow-up may be required for the following: hypocortisolism/cortisol withdrawal syndrome, hyperglycemia, and QTc interval prolongation.

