6.5.2.1 Adverse events

The incidence of on-treatment adverse events will be summarized by system organ class and preferred term using the MedDRA dictionary. A similar table will also be produced for the post-treatment period.

Similar summary will also be provided for AESIs summarized by category and preferred term (according to the risks specified in [Section 3.5.2.3](#)).

The primary objective of this study, the number and percentage of patients having any pasireotide s.c.-related adverse event and serious adverse event will also be separately summarized by system organ class and preferred term using the MedDRA dictionary for the on-treatment period.

AE listing will be generated for the overall AEs, pasireotide s.c. related AEs, SAEs, AESIs and deaths. These listings will cover both events that occur during the on-treatment and post-treatment period however, events that occur during the post-treatment period will be flagged.

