### 4.1 Data analysis general information

Data will be summarized and displayed by time intervals based visit windows rather than by a strict visit schedule.

Patients who discontinue treatment prior to the 3-year observation period, will have their safety and efficacy parameters reported according to the time window that corresponds to Day of last dose of pasireotide s.c. plus 90 days.

Continuous variables will be summarized by number of patients, mean, standard deviation, minimum, median and maximum. Categorical variables will be summarized by absolute and relative frequencies. Counts of missing values for both continuous and categorical variables will be reported.

The study is exploratory in nature and no formal hypothesis testing is planned.

Data will be analyzed according to the data analysis Section 6 of the study protocol (as amended on 20SEP2013) which is available in Appendix 16.1.1 of the CSR. Details are given in the following sections and more technical details are provided, as applicable, in Appendix 16.1.9 of the CSR. It is planned that the data from all study sites that participate in this study will be pooled, so that an adequate number of patients will be available for analysis.

Interim analyses will be performed every year as requested by Health Authorities. The first analysis will be conducted about 12 months after the first patient enters the study. After this first analysis there will be one interim analysis on a yearly basis. The recruitment period is expected to be approximately 8 years and each enrolled patient will be followed up for 3 years after enrollment. The final analysis will occur when all patients have completed the study. The same analysis will be performed at all analysis time points.

For each analysis a cut-off date will be set. All data collected up to this cut-off date will be included in the analysis.

Any data collected beyond the cut-off date for an analysis will not be included in the analysis. Only data with an assessment date or event start date (e.g. vital sign assessment date or start date of an adverse event) prior to or on the cut-off date will be included in the analysis. For example, if the cut-off date is 15 June 2010 then an AE starting on 13 June 2010 will be reported, whereas an AE with start date on 17 June 2010 will not be reported.

---

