Post-treatment AEs and post-treatment SAEs will be summarized by primary SOC, PT and maximum CTC grade in patients who discontinued pasireotide s.c. prior to completing the 3- year observation period.

In addition, (S)AEs leading to study discontinuation will be listed. Note that there is no respective flag on the eCRF. Therefore the listings will show all (S)AEs which were ongoing at the time of study discontinuation due to AE or which ended the day before.

Also summary on clinically notable AEs (patients who had grade 3/4 AEs, SAEs, AEs leading to discontinuation or other significant AEs) will be prepared for the subgroup of patients from German sites.

Specific groupings of AEs of special interest will be considered and the number of patients with at least one event in each grouping ("category") will be reported. Such groups consist of AEs for which there is a specific clinical interest in connection with pasireotide treatment (i.e. where pasireotide may influence a common mechanism of action responsible for triggering them) or AEs which are similar in nature (although not identical) within project defined group. The specific groupings of AEs as defined in the Attachment 9.2 AESI List (latest documentation available prior to database lock) will be used.

The following tables will be produced:

- AEs of special interest, regardless of relationship with pasireotide s.c., by category, preferred term and maximum CTC grade,
- SAEs of special interest, regardless of relationship with pasireotide s.c., by category, preferred term and maximum CTC grade,
- AEs of special interest, regardless of relationship with pasireotide s.c., by type (any AE, AE suspected to be related to pasireotide s.c., SAE, AE leading to discontinuation, AE requiring dose adjustment or study-drug interruption) and PT

---

Study Code: CSOM230B2410

- AEs of special interest, regardless of relationship with pasireotide s.c., by time interval of onset (0 to < 3 months, 3 to < 6 months, 6 to <9 months, etc.), category and preferred term.

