## 9.2 AESI LIST

Category	Adverse Event Term
AESI Bradycardia related AEs	Atrial conduction time prolongation (PT) Atrioventricular block (PT) Atrioventricular block complete (PT) Atrioventricular block second degree (PT) Atrioventricular dissociation (PT) Bradycardia (PT) Central bradycardia (PT) Conduction disorder (PT) Defect conduction intraventricular (PT) Electrocardiogram PQ interval prolonged (PT) Electrocardiogram PR prolongation (PT) Electrocardiogram QRS complex prolonged (PT) Electrocardiogram QT prolonged (PT) Long QT syndrome (PT) Paroxysmal atrioventricular block (PT) Sinoatrial block (PT) Sinus bradycardia (PT)
AESI Coagulation related AEs	Blood fibrinogen decreased (PT) Blood thrombin decreased (PT) Blood thromboplastin abnormal (PT) Blood thromboplastin decreased (PT) Coagulation factor IX level decreased (PT) Coagulation factor V level decreased (PT) Coagulation factor VII level decreased (PT) Coagulation factor X level decreased (PT) Coagulation factor decreased (PT) Hypofibrinogenaemia (PT) International normalised ratio abnormal (PT) Prothrombin level decreased (PT) Prothrombin time prolonged (PT) Prothrombin time ratio decreased (PT) Thrombin time prolonged (PT)
AESI Gallbladder and biliary related AEs	Bile duct necrosis (PT) Bile duct obstruction (PT) Bile duct stenosis (PT) Bile duct stone (PT) Bile output abnormal (PT) Bile output decreased (PT)

Study Code: CSOM230B2410

Category	Adverse Event Term
	Bile output increased (PT)
	Biliary cirrhosis (PT)
	Biliary colic (PT)
	Biliary dilatation (PT)
	Biliary dyskinesia (PT)
	Biliary dyspepsia (PT)
	Biliary fibrosis (PT)
	Biliary fistula (PT)
	Biliary ischaemia (PT)
	Biliary tract disorder (PT)
	Bilirubin conjugated abnormal (PT)
	Bilirubin conjugated increased (PT)
	Bilirubin excretion disorder (PT)
	Bilirubin urine present (PT)
	Bilirubinuria (PT)
	Blood alkaline phosphatase abnormal (PT)
	Blood alkaline phosphatase increased (PT)
	Blood bilirubin abnormal (PT)
	Blood bilirubin increased (PT)
	Blood bilirubin unconjugated increased (PT)
	Cholangiogram abnormal (PT)
	Cholecystectomy (PT)
	Cholecystitis (PT)
	Cholecystitis acute (PT)
	Cholecystitis chronic (PT)
	Cholecystogram intravenous abnormal (PT)
	Cholecystogram oral abnormal (PT)
	Cholelithiasis (PT)
	Cholelithiasis migration (PT)
	Cholelithiasis obstructive (PT)
	Cholestasis (PT)
	Deficiency of bile secretion (PT)
	Endoscopy biliary tract abnormal (PT)
	Gallbladder disorder (PT)
	Gallbladder enlargement (PT)

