AESI Pancreatitis related AEs	Abdominal compartment syndrome (PT) Blood trypsin increased (PT) Fat necrosis (PT) Hyperlipasaemia (PT) Lipase abnormal (PT) Lipase increased (PT) Pancreatic enzyme abnormality (PT) Pancreatic enzymes abnormal (PT) Pancreatic enzymes increased (PT) Pancreatitis (PT) Pancreatitis acute (PT) Pancreatitis haemorrhagic (PT) Pancreatitis necrotising (PT) Pancreatitis relapsing (PT) Peripancreatic fluid collection (PT)
AESI QT-prolongation-related AEs	Cardiac arrest (PT) Cardiac death (PT) Cardiac fibrillation (PT) Cardio-respiratory arrest (PT)

Study Code: CSOM230B2410

Category	Adverse Event Term
	Electrocardiogram QT interval abnormal (PT)
	Electrocardiogram QT prolonged (PT)
	Electrocardiogram repolarisation abnormality (PT)
	Long QT syndrome (PT)
	Loss of consciousness (PT)
	Sudden cardiac death (PT)
	Sudden death (PT)
	Syncope (PT)
	Torsade de pointes (PT)
	Ventricular arrhythmia (PT)
	Ventricular fibrillation (PT)
	Ventricular flutter (PT)
	Ventricular tachyarrhythmia (PT)
	Ventricular tachycardia (PT)

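### The SAP's list of adverse events of special interest has no category for five of the 18 event-type risks named in the protocol, and counts two QT terms as bradycardia

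*Protocol*

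**What the plan says.** Protocol 6.5.2.1, after describing the general adverse event tables, continues: "Similar summary will also be provided for AESIs summarized by category and preferred term (according to the risks specified in" Section 3.5.2.3). That section names nine important identified risks: "hypocortisolism/cortisol withdrawal syndrome, hyperglycemia, bradycardia, QTc interval prolongation, cholelithiasis, hematological abnormalities", then "increased liver enzymes, injection site reactions, and gastrointestinal disorders". It also names eleven important potential risks. These include "coagulation abnormalities, hypotension, hypocalcemia, gastrointestinal erosions/bleedings", allergic reactions/immunogenicity and tumor expansion, together with drug interactions and off-label use. It adds that the AESIs are not confined to these risks.

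SAP 8.4.1 takes its groupings from one place: "The specific groupings of AEs as defined in the Attachment 9.2 AESI List", in the version current before database lock. From these groupings it plans tables by category and maximum grade, the same for serious events, tables by type of event, and tables by time interval of onset. Attachment 9.2 has 13 categories. Its bradycardia category contains the run "Electrocardiogram QT prolonged (PT) Long QT syndrome (PT) Paroxysmal atrioventricular block (PT"), and the first two of these terms appear again in its QT-prolongation category. SAP Section 3, on changes to the planned analysis, reads as not applicable.

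**The concern.** The protocol fixes the AESI categories by reference to a named list of risks, and the SAP's attachment does not contain all of them. Long-term safety is the primary objective of this post-authorization study. The AESI tables are where a reader finds how many patients had at least one event for each named risk, how severe and serious the events were, and when they began. A risk without a category has no such row, and its events are spread over individual preferred terms.

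The bradycardia category has the opposite problem: it takes in events that belong to another named risk. The protocol requires QTcF/QTcB above 480 msec to be reported as an adverse event (Sections 3.5.2.5 and 3.5.2.10), so QT terms can be expected in the data. Each patient whose only event in the category is one of these terms would be tabulated as having a bradycardia-related event.

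**Working it through.** **Step 1: match risks to categories.** The left column is from protocol 3.5.2.3, the right from SAP Attachment 9.2.

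| Protocol risk | SAP category |
|---|---|
| *Identified* | |
| Hypocortisolism | Hypocortisolism |
| Hyperglycemia | Hyperglycemia |
| Bradycardia | Bradycardia |
| QTc prolongation | QT-prolongation |
| Cholelithiasis | Gallbladder and biliary |
| Hematological abnormalities | Low blood cell |
| Increased liver enzymes | Liver safety |
| Injection site reactions | Injection site reaction |
| Gastrointestinal disorders | **none** |
| *Potential* | |
| GH/IGF-1 decrease | Growth hormone deficiency |
| Hypothyroidism | Hypothyroidism |
| Pancreatitis | Pancreatitis |
| Coagulation abnormalities | Coagulation |
| Hypotension | Hypotension |
| Hypocalcemia | **none** |
| GI erosions/bleedings | **none** |
| Allergic reactions/immunogenicity | **none** (local injection-site terms only) |
| Tumor expansion | **none** |
| Drug interactions | none, not counted |
| Off-label use | none, not counted |

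Items: 9 + 11 = 20. Matched: 8 + 5 = 13. Unmatched: 20 − 13 = 7. Interactions and off-label use do not describe a type of event that a set of preferred terms would capture. Without them, 7 − 2 = 5 of 18 event-type risks have no category: 1 of 9 identified and 4 of 9 potential.

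**Step 2: see what the other tables supply.** SAP 8.4.1 tabulates patients by system organ class, preferred term and severity, counting a patient once per category. It lists separate summaries for related events, serious events, discontinuations and dose adjustments.

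- *Gastrointestinal disorders.* Protocol Section 1 itself names this as a system organ class. Its row gives a per-patient count. What is mainly missing is the table by onset interval (0 to <3 months, 3 to <6 months, and so on).
- *Hypocalcemia and GI erosions/bleedings.* No pooled row exists. Attachment 9.2 shows why one is needed: for other risks it gathers diagnoses and test findings together, such as thrombocytopenia with platelet count decreased.
- *Allergic reactions/immunogenicity.* The injection-site category includes hypersensitivity, rash, pruritus and urticaria at the injection site, but nothing systemic. Protocol 6.5.2 names immunological events among the safety assessments; the list in SAP 8.4 does not.
- *Tumor expansion.* Tumor volume is summarized as an efficacy variable (SAP 8.2.1.6). That is not a count of patients with an adverse event.

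**Step 3: compare the bradycardia and QT lists.** Bradycardia has 17 preferred terms and QT-prolongation has 18. They share two: Electrocardiogram QT prolonged and Long QT syndrome. That is 2/17 = 11.8% of the bradycardia terms. Removing them leaves 15 there and all 18 in the QT category.

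**Step 4: illustrate the excess.** No rate for these terms is given. Let *b* be the share of patients with a bradycardia-category event other than the two QT terms, and *q* the share with either QT term. If the two are independent, the tabulated share is 1 − (1 − *b*)(1 − *q*). Both rates are assumptions.

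| *b* | *q* | Tabulated | Ratio to *b* |
|---|---|---|---|
| 5% | 1% | 1 − 0.95 × 0.99 = 5.95% | 1.19 |
| 5% | 3% | 1 − 0.95 × 0.97 = 7.85% | 1.57 |
| 5% | 6% | 1 − 0.95 × 0.94 = 10.7% | 2.14 |

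With *b* from 2% to 10% and *q* from 1% to 6%, the ratio runs from 1.09 (10%, 1%) to 3.94 (2%, 6%). Without independence, the excess cannot exceed *q*, and it is zero if every patient with a QT term also has another bradycardia-category event.

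**The case against.** The case on the other side has real force.

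- *Gastrointestinal disorders is already tabulated.* A reader might infer that diarrhea and nausea, two of the three most frequent events in the pivotal trial, would go uncounted by risk. They would not: the system organ class row counts patients, with severity, relatedness and seriousness. This stands, and it leaves four potential risks as the main gap.
- *The list can still change.* The SAP uses the version current before lock. The SAP is dated 22 September 2023, and the Amendment 2 rationale planned the last follow-up visit for April 2024. One might say that the clause is no help because the 2023 SAP was updated for the final report, but the documents do not support that. The clause is a route to correction; it does not correct the attached list by itself.
- *The QT terms are duplicated, not moved.* A reader might infer that QT events are lost or misfiled. They are not, since both terms stay in the QT category. It is also fair that only 3 of the 17 bradycardia terms contain that word and most of the rest are conduction terms, and that overlap occurs elsewhere (Urine bilirubin increased is in both the gallbladder and liver groups). But the protocol names bradycardia and QTc prolongation as separate risks, and the SAP gives no reason for counting one under the other.
- *The SAP cites the protocol "as amended on 20SEP2013".* It is tempting to blame this, because Amendment 2 revised the AESI list in 2016. The pointer is to protocol Section 6, the only Section 6 change that Amendment 2 lists is to 6.6, and no document states a cause.
- *Calcium is not on the laboratory list.* A reader might conclude that hypocalcemia cannot be detected. It can still be reported as an adverse event; which tests are collected is a separate question from grouping.
- *AESIs are not limited to the named risks.* That wording allows additions. It does not allow omissions.

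**Conclusion.** The point holds. Attachment 9.2 departs from protocol 6.5.2.1 and 3.5.2.3, and the SAP does not declare it. Five of 18 event-type risks have no category. For four potential risks (hypocalcemia, GI erosions/bleedings, allergic reactions/immunogenicity, tumor expansion) the adverse event tables offer no pooled per-patient count elsewhere. For gastrointestinal disorders, an identified risk, the loss is mainly the onset-interval table. The count of 18 leaves out drug interactions and off-label use; counted literally, 7 of 20 items have no category.

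The bradycardia category would also count patients whose only event in it is a QT term. The direction is certain for any such patient; the size is not known, and the ratios of 1.09 to 3.94 rest wholly on assumed rates and independence.

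The consequence is limited. The primary endpoint, related adverse events and serious adverse events, does not use these groupings. There is no hypothesis test. The three risks that the protocol singles out for possible targeted follow-up (hypocortisolism, hyperglycemia, QTc prolongation) all have categories. The omitted events still appear under their own preferred terms.

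**What to change.** In the AESI list used at database lock:

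1. Add categories for hypocalcemia, gastrointestinal erosions/bleedings, allergic reactions/immunogenicity and tumor expansion, with their preferred terms.
2. Add a gastrointestinal disorders category, or state that the system organ class row serves and add the onset-interval table for it.
3. Remove Electrocardiogram QT prolonged and Long QT syndrome from the bradycardia category. The QT category needs no change.
4. Consider adding amylase and activated partial thromboplastin time (APTT) terms. The protocol's laboratory lists include α-amylase and APTT but not lipase. The pancreatitis group has "Lipase abnormal (PT) Lipase increased (PT") and general pancreatic enzyme terms but none specific to amylase. The coagulation group covers prothrombin time but has no APTT term. This is a refinement; SAP 8.4.2 gives collected laboratory values shift tables in any case.
5. Record in SAP Section 3 any remaining departure from protocol 3.5.2.3, including how drug interactions and off-label use are handled.

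Steps 1 and 2 would raise the categories from 13 to 18 (17 if the system organ class row serves for gastrointestinal disorders). The cost is a revised attachment, a short entry in Section 3 and reprogrammed groupings of events already coded. No new data and no patient procedures are needed.
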